5 REGULATORY ASPECTS AND SAFETY

5.1 Local regulations / Declaration of Helsinki

This research project will be conducted in accordance with the protocol, the Declaration of Helsinki [3], the principles of Good Clinical Practice, the Human Research Act (HRA) and the

Human Research Ordinance (HRO) [1] as well as other locally relevant regulations. The Project Leader acknowledges his responsibilities as both the Project Leader and the Sponsor.

5.2 Notification of safety and protective measures (HRO Art. 20)

The project leader is promptly notified (within 24 hours) if immediate safety and protective measures have to be taken during the conduct of the research project. The Ethics Committee will be notified via BASEC of these measures and of the circumstances necessitating them within 7 days.

5.3 Serious events (HRO Art. 21)

If a serious event occurs, the research project will be interrupted and the Ethics Committee notified on the circumstances via BASEC within 7 days according to HRO Art. 21¹.

5.4 Procedure for investigations involving radiation sources

Not applicable

5.5 Amendments

Substantial changes to the project set-up, the protocol and relevant project documents will be submitted to the Ethics Committee for approval according to HRO Art. 18 before implementation. Exceptions are measures that have to be taken immediately in order to protect the participants.

5.6 End of project

Upon project completion or discontinuation, the Ethics Committee is notified within 90 days. Biological material (serum samples) and data from the questionnaire will be kept for 10 years.

5.7 Insurance

In the event of project-related damage or injuries, the Sponsor will be liable, except for damages that are only slight and temporary; and for which the extent of the damage is no greater than would be expected in the current state of scientific knowledge (Art. 12 HRO).

6 FURTHER ASPECTS

6.1 Overall ethical considerations

Our study aims to generate robust epidemiological data on a special population that is at risk because of their occupation. Social distancing and contact avoidance rules may not be possible in the practice of policemen's work. Conversely, the risk of exposure in this population may be increased because of emergency calls for violence or because of actions against groups of people who ignore or demonstrate against lockdown measures [29-31]. Considering that 80% to 90% of individuals infected with SARS-CoV-2 are undocumented or asymptomatic, the risk of exposure of police officers when entering the scene is unknown. These arguments justify the necessity of a special population seroprevalence survey.

¹ A serious event is defined as any adverse event where it cannot be excluded, that the event is attributable to the sampling of biological material or the collection of health-related personal data, and which:

- a. requires inpatient treatment not envisaged in the protocol or extends a current hospital stay;
- b. results in permanent or significant incapacity or disability; or
- c. is life-threatening or results in death.

Serological testing has a role in identifying people with milder disease who have been missed by other methods. Serological surveys address the problem of overfitting the trajectories of the epidemic curve based on the number of symptomatic infections instead of the total number of infections, which includes asymptomatic infections [9]. Our study will generate data while we conduct the investigation (at cross-sectional time points) and immediately after we end it (cohort data). Thus, epidemiological data will be readily available and will help refine epidemic trajectory models. Population immunity levels are required to inform disease control policies. The data will represent a measurement of those who are susceptible to infection, quantify the need for vaccination, and aid policies for decision making about vaccination strategies.

The seroprevalence survey will generate data that are useful for police departments in other cantons in Switzerland and in other countries. The methodology can be easily implemented in other institutions, and hence allows comparisons of preventive measures in association with seroprevalence results between cantons and nations.

The duration of both antibody persistence and neutralizing capacity over time is unknown. Because we are generating a cohort, we are able to monitor antibody levels over 1 year. Similarly, we are able to investigate the neutralizing capacity in study participants who repeatedly test positive for SARS-CoV-2. These data are important to evaluate possible immunity over time, both after virus exposure and – if available – after vaccination.

The burden and time effort for participants is minimal. We are not using genetic data, nor are we investigating a vulnerable patient population. Therefore, we are convinced that there is an overall fair balance for the study participant.

6.2 Risk-Benefit Assessment

This study poses minimal risk to participants, requiring the collection of one serum sample per visit (each tube has a volume of 9 mL). If there is a contraindication to venipuncture, the subject will not be recruited in the study. We have included means to counterbalance social pressure from superiors or peers to participate in the study.

There is no immediate benefit to the project participant. The data collected will help improve and guide efforts to understand the extent and risk of COVID-19 virus among police officers. In addition, it may be important for an individual to know whether they were exposed to SARS-CoV-2 prior to or during the study. The use of convalescent plasma has been proposed for the treatment of COVID-19, recently [32]. With our study strategy, potential antibody donors, and those with neutralizing antibody capacity can be identified. The study strategy may be transferred to large scale populations, and hence, generate a higher number of donors. Thus, the results of the project could benefit future patients.

It is anticipated that a vaccine will be available in the future. Study participants can compare the immune response and vaccine efficacy/synergism pre- and post-vaccination by using the stored serum sample from this study and a serum sample taken after vaccination. However, such a scenario will require a new research and ethic proposal.

6.3 Rationale for the inclusion of vulnerable participants

The study includes healthy volunteers, because the study focuses on employees of the cantonal police of Bern and not on individuals with a disease.

7 QUALITY CONTROL AND DATA PROTECTION

7.1 Quality measures

The study protocol is aligned with that of the WHO for population-based age-stratified sero-epidemiological investigations, adapted for the specific population and geographic region in our study [25]. Data and serum results will be collected in a standardized format according to the

questionnaires and tools in the WHO protocol to assist with data harmonization and comparison of results.

The study team consists of a collaborative consortium of the core research team, the Interregionale Blutspende SRK, the police department of the canton of Bern, and the Clinical Trial Unit (CTU) of Bern for data management and statistical analysis. In addition, highly qualified study nurses and serology laboratory technicians at our institution (IFIK) support our team. Members of the team are trained in the collection and transportation of serum specimens, safe handling practices, and spill decontamination procedures. They are also trained in infection prevention and control procedures (standard contact and droplet precautions) and in Good Clinical Practice.

Results of antibody testing will directly and automatically be transferred to the databank (REDCap) to avoid entry mistakes. Study participants will enter the response of the questionnaire into the REDCap system. A study nurse will verify data and contact study participants in case of entry mistakes or missing data. Hence, the study is accompanied by project personnel trained on all project related aspects.

7.2 Data recording and source data

Project data will be recorded in a central database (Research Electronic Data Capture, REDCap) hosted by our collaborator, the CTU of the University of Bern. The databases are highly secured and fulfil all requirements of the Swiss Human Research Act. Different data access privileges will be set for different user types (data clerks, data managers, PI). Study participants will be asked to complete an online questionnaire that covers information on demographics and possible COVID-19 exposure or infection. Questionnaires and database will be designed in order to minimize data capture errors, using drop-down menus, data range limits and data type protection where possible. Returned questionnaires will be reviewed for completeness and responses electronically stored in the REDCap database. Routine data checks will be performed. Also results from serology analyses will be automatically entered into REDCap. The PI is responsible for assuring that the data collected is complete, accurate and recorded in a timely manner. Security and back-up of data storage will be guaranteed by CTU, University of Bern. To access this source, user authentication and a password will be required. Data will be accessible according to Open Research Data and FAIR principles when corresponding manuscripts are published.

7.3 Confidentiality and coding

Project data will be handled with uttermost discretion and is only accessible to authorized personnel who require the data to fulfil their duties within the scope of the research project. Each study participant will be assigned a unique study identification number (barcode) for the labelling of questionnaires and serum specimens. This code will be coupled with a second code that indicates the visit number and the result assignment (serum sample or questionnaire, see below coding). On the CRFs and other project specific documents, participants are identified by the unique participant number (barcode). In the databank (REDCap), the study participant's email address is collected, too. Therefore, **the databank is not completely coded**, because study participants may be potentially identified if they use an e-mail address displaying their names. The use of e-mail addresses is required because online questionnaires will be distributed through an automated process. This is to avoid potential mistakes that are likely to be generated when using a manual system, due to the large number of participants recruited and followed up at each study visit. The CRFs in this trial are implemented electronically using a dedicated electronic data capturing (EDC) system (REDCap, <https://www.project-redcap.org/>). Questionnaires for patients will be prepared in electronic format and will be accessible through a personal link. The personal link will be sent to the patient's email address. Patients' email address will be therefore collected into REDCap but this field will be tagged as "Identifier field" and thus will be automatically removed from data exports. Considering that we expect 1'000 study participants and at least 5 visits for each study participant, there is a high risk of mistakes

if data are transferred manually. **After termination of the study, and confirmation of the completeness of the data set, the e-mail address will be removed from the data bank, to ascertain a completely coded databank.**

The server hosting the EDC system and the database is kept in a locked server-room at the CTU Bern. Only the system administrators have direct access to the server and back-up tapes. A role concept with personal passwords (site investigator, statistician, monitor, administrator) regulates permission for each user to use the system and database as he/she requires.

All data entered into the CRFs are transferred to the database using Transport Layer Security (TLS) encryption. Each data point has attributes attached to it identifying the user who entered it with the exact time and date. Retrospective alterations of data in the database are recorded in an audit table. Time, table, data field and altered value, and the person are recorded (audit trail). A multi-level back-up system is implemented. Back-ups of the whole system including the database are run internally several times per day and on external tapes once a day. The back-up tapes are stored in a secure place in a different building.

Coding: Each study participant will be assigned a unique study identification number (barcode) for the labelling of questionnaires and serum specimens. We will use a barcode system that allows scanning and printing out stickers. This barcode will be coupled with a second code that indicates the visit number and the result assignment. Study-related data of the patient will be collected in a coded manner. The names of the patients will not be disclosed. As outlined above, e-mail addresses provided by the study participants will be used. Depending on the provided e-mail address, the patient's names may be identifiable. After termination of the study, and confirmation of completeness of data, e-mail addresses will be removed, and only coded data used.

Biological material: Biological material (serum sample) is not identified by participant name but by a unique participant number (barcode, see paragraph above). Biological material (serum sample) is appropriately stored in a restricted area only accessible to authorized personnel. Serum samples will be stored at IFIG (-80°C) and at Interregionale Blutspende SRK (-30°C). The diagnostic and research laboratories of the IFIG and at Interregionale Blutspende SRK have the required government permits to operate a diagnostic service for clinical specimens of human origin, including storage of such clinical specimens; furthermore, they are accredited to the ISO/IEC 17025 Standard. All laboratory equipment throughout the entire Institute, including freezers and microbiological safety cabinets, is covered by contracts for planned preventative maintenance. Where appropriate, equipment is also monitored by laboratory staff in accordance with the comprehensive Quality Management and Safety Management systems in place at the Institute. All visitors, irrespective of their business, are required to sign a confidentiality agreement before being granted access to the building (they also sign when leaving the institute).

7.4 Retention and destruction of study data and biological material

At *interim* and final analyses, data files will be extracted from the database into statistical packages to be analyzed. After database lock, the status of the database is recorded in special archive tables. The sponsor (PI) will keep the Trial Master File, the extracted data, the meta data and *interim/final* reports for at least 10 years after project termination. Serum samples will be stored for at least 10 years after project termination. The storage of serum samples depends on the consent for further use (see 5.6). In line with the study information and consent form, study participants are invited to sign additional consent for further use of their serum samples. If there is no consent for further use or withdraw of consent during the study period, serum samples will be destroyed after termination of the project. If there is consent for further use, serum samples will be stored in our biobank for at least 10 years after project termination.

8 FUNDING / PUBLICATION / DECLARATION OF INTEREST

The project will be financially supported by the Police Department of the Canton Bern, and logistically, with personnel and materials by the Institute for Infectious Diseases of the University of Bern and the Interregionale Blutspende SRK Bern.

Appendix 1: Schedule of assessments

Time (months)	0-3	3-6	+0.5 & +1	6-9	+0.5 & +1	9-12	+0.5 & +1	12-15	+0.5 & +1	15-18	+0.5 & +1
Visit	Study information & candidates registration	1 st visit baseline		2 nd visit		3 rd visit		4 th visit		5 th visit	
Oral and written Information	+										
Candidates registration on study website	+										
Written consent		+									
Check inclusion-/exclusion criteria			+								
Online Questionnaire		+		+		+		+		+	
Blood Sampling		+		+		+		+		+	
Procedures (serum testing)		+		+		+		+		+	
Additional questionnaire for seropositive participants			+		+		+		+		+
Confirmatory blood sampling			+		+		+		+		+
Procedures (confirmatory serum testing)			+		+		+		+		+

Appendix 2: The categorization of variables

Parameter	Definition	Source of data to calculate the parameters
Cumulative incidence	The proportion of individuals with seropositivity	Laboratory result
Age- and gender specific attack rate	The proportion of individuals per age and gender strata with seropositivity	Laboratory result Questionnaire
Symptomatic proportion of cases	The proportion of individuals with seropositivity who showed symptoms or signs of COVID-19 infection (+/- confirmed PCR result in the past)	Questionnaire
Asymptomatic proportion of cases	The proportion of individuals with seropositivity who showed no symptoms or signs of COVID-19	Questionnaire
Attack rate in risk group (health-related data) (Persons over 65 years are not included because retirement is expected at this age in the study population).	Study participants with one or more of the following risk factors: diabetes, arterial hypertension, cardiovascular disease, chronic pulmonary disease, immuno-compromised because of host diseases or because of medical treatment, cancer, obesity (BMI > 30 kg/m ²)	Laboratory result Questionnaire
Activity related cumulative incidence	The proportion of individuals with seropositivity in the following 2 groups: Group 1: Police officers with fieldwork activity and frequent population contact. Group 2: office and administration occupation with low population contact.	Laboratory result Questionnaire
Geography related cumulative incidence	The proportion of individuals with seropositivity in the following 2 groups: Group 1: occupation in cities (Bern, Thun, Biel) Group 2: occupation in rural area of Bern or in cities but not belonging to group 1.	Laboratory result Questionnaire
Sub-study in seropositive study participants		
Parameter	Definition	Source of data to calculate the parameters
Serological response to infection	The change in serum level of specific antibodies to COVID-19 virus (increase in antibody titres)	Laboratory result over time
Seropositive result confirmation (specificity)	Seropositive result at baseline or seroconversion during the study year that will be confirmed with two additional serum samples, two and four weeks after the positive antibody result.	Laboratory result
Work or social environment-related exposure	Study participants perception of possible COVID-19 exposure	Questionnaire

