1 BACKGROUND AND PROJECT RATIONALE

1.1 Background

Knowledge of diagnostic tests for SARS-CoV-2 is still evolving, and their correct use and an understanding of the results is important for both clinical and epidemiological studies. Two types of diagnostic tests commonly in use for SARS-CoV-2 infections are reverse transcriptase polymerase chain reaction (RT-PCR) and anti-SARS-CoV-2-antibodies [5]. Although SARS-CoV-2 is an antigenically variable pathogen, serological surveys provide powerful evidence during a pandemic. Serological testing has an increasing role in identifying convalescent cases and persons with nonspecific mild respiratory symptoms or no symptoms who have recovered from SARS-CoV-2 without being diagnosed [6]. The current prediction is that approximately 80% to 90% of people are undocumented or asymptomatic, hence facilitating the rapid spread of the virus [7]. Because serological surveys are able to identify both asymptomatic and symptomatic cases that have passed the acute phase of COVID-19, they are paramount to generating key data on the epidemiology of SARS-CoV-2 [8,9].

The Centers for Disease Control and Prevention and others have clearly indicated the importance of seroprevalence surveys on COVID-19 [8]. Recently, several institutions have performed different types of serological surveys [10]. Results from Geneva, Switzerland, indicate a seroprevalence of 3.1% to 9.7% over 3 weeks testing [11]. Nonetheless, there are considerable differences of COVID-19 seroprevalence both within a country and between countries. A direct comparison of results is difficult because of different study types, different population selections and hence potential bias, and the use of different (mostly not validated) tests. Epidemiological antibody studies are typically categorized as (i) large-scale geographic, (ii) community-level, and (iii) special population seroprevalence surveys [8]. This project is a special population seroprevalence survey.

While the majority of exposed workers are employed in healthcare sectors, other occupational sectors also have high proportions of exposed workers [12]. A recent study suggested that protective services (e.g., police officers and others) are the third most common exposed group, after healthcare support workers and healthcare practitioners. Approximately 30% of protective services personnel are exposed to COVID-19 risk at least once per week [12].

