2.2 Primary and secondary endpoints

Primary endpoint: The variable of primary interest is **COVID-19 seropositivity**. This variable is measured at five time points over the one-year study period. The following baseline factors may have an influence on the primary endpoint and will be obtained: (i) pre-existing comorbidities, (ii) rural versus city distribution of working place, and (iii) office work versus field work.

Secondary endpoints: We will assess the proportion of symptomatic and asymptomatic cases among seropositive participants. We will calculate the attack rate in different subgroup. These include (i) study participants with health-related risk factors (age>50 and age>60 years, diabetes, arterial hypertension, cardiovascular disease, chronic pulmonary disease, immune-compromised status due to host diseases, medical treatment, cancer, obesity), (ii) activity-related subgroups (i.e. fieldwork vs office activity), (iii) geography-related subgroups (i.e. city vs rural areas). In follow-up visits, the antibody titers (i.e. dynamic) and the neutralization capacity will be assessed. Thereby we will determine the change in serum levels of SARS-CoV-2 antibodies over time in seropositive participants.

2.3 Project design:

This is a single center special population (i.e. police officers of the canton of Bern) seroprevalence survey. It is a repeated cross-sectional investigation in the canton of Bern combined with a longitudinal cohort study with serial sampling of the included study participants. The protocol is aligned with the one of seroprevalence studies recommend by the WHO [25].

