3.3 Study procedures

The overall project will span an 18-month period. We anticipate starting the study in December 2020, with a baseline visit and first sampling in January 2021. Sample collection will be terminated in February/March 2022. Hence, the project duration for each study participant will be 1 year.

The study protocol is aligned with that of the WHO for population-based age-stratified sero-epidemiological investigations. We adapted the protocol for our specific population and for the geographic region of the canton of Bern [25]. Data and serum results will be collected in a standardized format according to the questionnaires and tools in the WHO protocol to assist with data harmonization and comparison of results.

Upon signed consent, each study participant will be assigned a study identification number (code) for the labelling of questionnaires and serum specimens.

Each participant recruited for the investigation will be asked to complete an online questionnaire at their convenience within time frame of 2 to 3 weeks, which covers information on demographics and possible COVID-19 exposure or infection (see point 5 in the BASEC application: "CASE REPORT FORM"). Returned questionnaires will be reviewed for completeness and responses electronically stored in a database (REDCap).

A serum sample will be collected from each participant upon recruitment into the investigation (visit 1, baseline). According to the study participant's preference, the study team will conduct police station visits to collect specimens OR study participants will visit the Interregionale Blutspende SRK for blood sampling. Serial sampling is then to be conducted every 3 months (i.e., five sampling time points over 1 year), meaning that each participant will be asked to attend a total of 4 follow-up visits.

Figure 1 describes when data and specimens will be collected according to the study plan permitted timeframe for each visit. A visit corresponds to one blood sampling appointment. A visit is defined as a time frame between 2 and a maximum of 3 weeks. Dates for appointments will be randomly alternated between police stations in cities and those in rural areas to preserve equal temporal distribution of visits between these areas. Results from microbiological analyses will be entered into REDCap. A schedule of assessments is also illustrated in appendix 1.

[figure not shown]

Figure 1: Schematic overview of the study procedure

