In serum samples with positive antibody test, quantification of neutralizing antibodies will be performed at the IFIG. They will be measured by pre-incubating serial dilutions of baseline and convalescent serum with 200 to 400 plaque forming units (PFU) of SARS-CoV-2, after which a PFU reduction assay will be performed on Vero-E6 cells. After 2 days, cells will be fixed and stained with crystal violet to analyse the neutralizing capacity of antibodies generated towards SARS-CoV-2, as previously described [26].

The results of Anti-SARS-CoV-2-Test of will be communicated to study participant via e-mail within 2 weeks of blood sampling. The results of neutralization capacity will be communicated at the end of the study period. This experimental assay will be performed in the research laboratory with all positive samples during one month, at the end of the study period.

Seropositive participants or participants with a positive SARS-CoV-2 test in the past (PCR or antigen test) will be asked to complete an additional questionnaire that investigates possible contacts (i.e., working versus private environment) and sources of transmission (see point 5 in the BASEC application: "CASE REPORT FORM").

Seropositive participants or vaccinated participants will be contacted by the study team within 4 weeks after laboratory result, for one additional blood sampling that investigates neutralization capacity. Seropositive participants with vaccination will be contacted twice. Figure 2 illustrates the sampling scheme.

Antibodies	Vaccine	No. of blood sampling in 1 year
		
negative	no	5 baseline + every 3 months
positive	no	6 baseline + every 3 months + 1 sampling
negative	yes	6 baseline + every 3 months + 1 sampling
positive	yes	7 baseline + every 3 months + 2 samplings

Figure 2: Schematic overview of the blood sampling over one year

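### The symptomatic share among seropositives is a crude count with no seronegative comparison, so symptoms from other causes and positives not due to infection distort it, in opposite directions

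*Combined protocol and SAP*

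**What the plan says.** Section 2.2 names the measure as a secondary endpoint: "We will assess the proportion of symptomatic and asymptomatic cases among seropositive participants". Appendix 2 defines the two halves. A symptomatic case falls under "The proportion of individuals with seropositivity who showed symptoms or signs of COVID-19 infection", with a past PCR result optional; an asymptomatic case falls under "The proportion of individuals with seropositivity who showed no symptoms or signs of COVID-19". The source for both is the questionnaire. Neither row gives a symptom list, a recall period, a seronegative comparator or a restriction to confirmed positives, and neither says which of the two antibody assays makes a person seropositive.

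Section 4.1 adjusts seroprevalence for false positives and false negatives. It plans no adjustment of the symptomatic share.

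On data collection, section 3.3 says "Each participant recruited for the investigation will be asked to complete an online questionnaire at their convenience" and describes the content as one "which covers information on demographics and possible COVID-19 exposure or infection". Appendix 1 marks this questionnaire at all five visits. Participants who are seropositive or have had a positive test "will be asked to complete an additional questionnaire that investigates possible contacts" and sources of transmission. The questionnaires themselves are in the ethics application, not in these documents.

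Section 3.3 also plans repeat sampling 2 and 4 weeks after a first positive result, and pairs an anti-nucleocapsid test with an anti-spike test so that vaccine-derived antibodies can be recognised.

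**The concern.** Serology shows that an infection occurred. It does not show that a symptom reported on a questionnaire came from that infection. Section 1.1 itself refers to "persons with nonspecific mild respiratory symptoms or no symptoms" among those whom serology identifies, and symptoms of that kind also have other causes. As Appendix 2 is written, a seropositive officer whose only symptoms had another cause would be classed as symptomatic.

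The two shares are complements, so whatever is added to one is taken from the other. Sections 1.1 and 6.1 argue for serosurveys partly on the ground that infections without recognised symptoms are missed by other methods. The asymptomatic share speaks directly to that argument, and a reader of the report could not tell how much of the symptomatic share is background.

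**Working it through.** The plan states no expected symptomatic share, so there is no figure to reproduce.

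**Inputs from the documents**
- Participants: 1,000 (section 4.1).
- Seroprevalence: 2% at the start, 10% at the end (sections 2.1 and 4.1).
- Sensitivity 97%, specificity at least 99% (section 4.1); manufacturer's specificity 99.81% (section 3.3).

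**Assumed, because the documents do not give them**
- True symptomatic share s: 20%, 50% or 60%.
- Background symptom rate b in the uninfected: 10% to 30%.
- Background symptoms occur independently of infection.

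**Step 1. All positives are true infections.** Crude share = s + (1 − s)b, so the excess is (1 − s)b.

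| s | b | Crude symptomatic | Crude asymptomatic |
|---|---|---|---|
| 50% | 10% | 0.50 + 0.50 × 0.10 = 55% | 45% |
| 50% | 20% | 0.50 + 0.50 × 0.20 = 60% | 40% |
| 50% | 30% | 0.50 + 0.50 × 0.30 = 65% | 35% |
| 20% | 20% | 0.20 + 0.80 × 0.20 = 36% | 64% |
| 60% | 20% | 0.60 + 0.40 × 0.20 = 68% | 32% |

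The excess is larger when few infections are symptomatic.

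**Step 2. Some positives are not infections.** With PPV the fraction of counted positives who were infected, crude = PPV × [s + (1 − s)b] + (1 − PPV) × b.

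At 2% prevalence and 99% specificity, true positives are 0.02 × 0.97 = 0.0194 and false positives 0.98 × 0.01 = 0.0098. PPV = 0.0194/0.0292 = 66.4%, with about 29 positives in 1,000.
- s = 60%, b = 20%: 0.664 × 0.68 + 0.336 × 0.20 = 52%, below the true 60%.
- s = 20%, b = 20%: 0.664 × 0.36 + 0.336 × 0.20 = 31%, above the true 20%.

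At 99.81% specificity, PPV is 91.2%. With s = 60% the crude share is 59% at b = 10% and 64% at b = 20%. Vaccine-derived positives, if counted, enter the formula in the same way as false positives.

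**Step 3. Which correction recovers s.** Take true infections with s = 60%, b = 20%, crude 68%.
- Plain subtraction: 68% − 20% = 48% = s(1 − b), which overcorrects.
- (0.68 − 0.20)/(1 − 0.20) = 60% = s.

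With unconfirmed positives the second formula returns PPV × s: (0.519 − 0.20)/0.80 = 40%. The restriction to confirmed infections is therefore part of the correction.

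**Step 4. Can b be estimated?** At least about 1,000 × (1 − 0.10) = 900 participants would be uninfected. Missed infections make up about 0.06% of seronegatives at 2% prevalence and 0.3% at 10%, so contamination of b is negligible.

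**Step 5. Price in precision.** The hypothesised rise of 8 points gives roughly 80 seroconverters in 1,000, ignoring dropout and imperfect sensitivity. At a crude 60%, the standard error is √(0.60 × 0.40/80) = 0.0548, or ±10.7 points. With b = 20% estimated from 900, its standard error is √(0.20 × 0.80/900) = 0.0133. The corrected share, (0.60 − 0.20)/0.80 = 50%, has standard error √[(0.0548/0.80)² + (0.40 × 0.0133/0.80²)²] = 0.069, or ±13.5 points.

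**The case against.** A reader might infer that the reported symptomatic share will be too high. The documents do not support that as a general statement. They give no background rate, and step 2 shows that at the plan's own 2% prevalence and 99% specificity the net error can be downward. Repeat sampling would limit false positives, but the Appendix 2 row does not say that it uses confirmed positives only. Nor does it exclude vaccine-derived antibodies. This objection stands, and it is why the upward direction is claimed only for confirmed infections.

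A reader might also infer that the seronegative data are already in hand. That is reasonable but not stated. The main questionnaire goes to everyone and covers possible infection, whereas the additional one is described in terms of contacts and transmission. If symptom detail were asked only in the latter, no comparison rate would exist. The unseen forms may also define symptoms, dates or attribution more tightly than Appendix 2 does.

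A same-interval correction does not suit everyone. Baseline positives, sampled in January 2021, may have been infected at any earlier time, and someone positive at several visits is not a new case at each. Equal reporting is also an assumption. Results are e-mailed within 2 weeks of sampling while questionnaires have a window of 2 to 3 weeks, so some participants may answer knowing their result. These limits stand and shape the fix.

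Finally, the measure is descriptive and appears in none of the section 2.1 objectives. With about 19 true positives at baseline (1,000 × 0.0194), the 95% Wilson interval at a 50% share is 29.5% to 70.5%, wider than the illustrated shift of 5 to 15 points. By 97 true positives (1,000 × 0.10 × 0.97) it narrows to 40.2% to 59.8%, and the shift is no longer hidden by sampling error.

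**Conclusion.** The point holds as a modest improvement to a secondary endpoint. Among confirmed infections the crude definition raises the symptomatic share, and lowers the asymptomatic share, by (1 − s)b: 5 to 15 points for a true 50% at an assumed background of 10% to 30%. The size rests on that assumed range, and the formula on independence of background symptoms and infection. If unconfirmed or vaccine-derived positives are included, the net direction is open. In either case the crude figure cannot be interpreted without the seronegative rate. The primary endpoint and the sample size are not affected.

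**What to change.** 1. In Appendix 2 and section 4.1, compute the symptomatic and asymptomatic shares in confirmed, anti-nucleocapsid-positive participants, counting each person once. Name the symptom items and the recall period.
2. For participants who seroconvert between visits, report the same symptom proportion over the same interval in participants who stay anti-nucleocapsid negative. Give (observed − b)/(1 − b) with a bootstrap confidence interval next to the crude share, and state the assumptions that background symptoms are independent of infection and equally reported in both groups.
3. For baseline positives, show the crude share beside the rate in baseline seronegatives over the same recall period. Do not treat that period as a 3-month interval.
4. Confirm that the questionnaire sent to all participants at each visit contains the symptom items. If it does not, report the crude share with this limitation stated.

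If item 4 is confirmed, the cost is a little more analysis with no new visits or samples, and a wider interval for the corrected share (in the example above, ±13.5 rather than ±10.7 points).
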